#### 5.4.3 C-SSRS

The C-SSRS responses will be mapped to Columbia- classification algorithm of suicide assessment (C-CASA). The incidence of new or worsening suicidal ideation or suicidal behavior will be summarized for treatment group by core study treatment (placebo and elenbecestat total) and combined total. The clinical assessment of suicidal thinking and behavior will also be summarized for treatment group by core study treatment (placebo and elenbecestat total) and combined total. Categorical variables will be summarized by number (percentage) of subjects.

#### 5.4.4 Laboratory Values

Laboratory results will be summarized using Système International (SI) units, as appropriate. For all quantitative parameters, the actual value and the change from baseline to each post-baseline visit will be summarized by visit for treatment group by core study treatment (placebo and elenbecestat total) and combined total using descriptive statistics. The end of treatment visit and 12 week Follow-up visit are also included, as appropriate. Qualitative parameters will be summarized using frequencies (number and percent of subjects), and changes from baseline to each post-baseline visit will be reported using shift tables. Percentages will be based on the number of subjects with both non-missing baseline and relevant post-baseline results.

Laboratory test results will be assigned a low/normal/high (LNH) classification according to whether the value was below (L), within (N), or above (H) the laboratory parameter's reference range. Within-treatment comparisons for each laboratory parameter will be based on 3-by-3 tables (shift tables) that compare the baseline LNH classification to the LNH classification at each post-baseline visit and at the end of treatment visit and 12 week Follow-up visit.

The Sponsor's Grading for Laboratory Values ([Appendix 13.1](#)) presents the criteria that will be used to identify subjects with treatment-emergent markedly abnormal laboratory values (TEMAV). Except for phosphate, a TEMAV is defined as a post-baseline value with an increase from baseline to a grade of 2 or higher. For phosphate, a TEMAV is defined as a post-baseline value with an increase from baseline to a grade of 3 or higher. The incidence of TEMAVs will be summarized for treatment group by core study treatment (placebo and elenbecestat total) and

combined total. When displaying the incidence of TEMAVs, each subject will be counted once in the laboratory parameter high and low categories, as applicable.

Lymphocyte subset parameters (ie, CD4 [T helper cells], CD8 [cytotoxic T cells], CD19 [B cells], CD16/CD56 [natural killer cells] and CD14 [macrophages], and regulatory T cells) will be summarized in the same manner as other laboratory parameters.

#### 5.4.5 Vital Signs

Descriptive statistics for vital signs parameters (ie, systolic and diastolic blood pressure (BP), pulse, respiratory rate, temperature, weight), and changes from baseline will be presented by visit for treatment group by core study treatment (placebo and elenbecestat total) and combined total.

In addition, frequency counts of clinically notable vital signs will be summarized for treatment group by core study treatment (placebo and elenbecestat total) and combined total. Table 1 presents the clinical notable ranges.

Table 1: Clinical Notable Ranges for Vital Signs

Vital Sign	Criterion for Low	Criterion for High
Pulse (bpm)	< 40	> 120
Temperature (°C)	< 36	> 38
Weight (kg)	< 45	> 100
Systolic BP	< 90	> 160
Diastolic BP	< 50	> 100

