## 5.4 Safety Analyses

Safety analysis will be performed similarly to the Core Study. All safety analyses will be based on OLE-SAS. The incidence of AEs, out-of-normal-range laboratory safety test variables, abnormal ECG findings, out-of-range vital signs, suicidality (Columbia Suicide Severity Rating Scale(C-SSRS)), and changes from baseline in laboratory safety test variables, ECGs, safety MRI, vital sign measurements, and cognitive decline assessment such as MMSE will be summarized by using descriptive statistics. The OLE baseline is used for all safety analyses.

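### Clinically notable vital signs are counted on absolute limits alone, so the subject-level count mixes pre-existing with new out-of-range values and misses large weight loss in all but light subjects

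*SAP*

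**What the plan says.** SAP Section 5.4.5 gives two displays of vital signs. The first is descriptive statistics of the values "and changes from baseline will be presented by visit for treatment group by core study treatment"; weight is among the parameters. The second is a count: "frequency counts of clinically notable vital signs will be summarized for treatment group by core study treatment". Its criteria come from one place: "Table 1 presents the clinical notable ranges". For weight the table row reads "Weight (kg) < 45 > 100", for systolic pressure "Systolic BP < 90 > 160" and for diastolic pressure "Diastolic BP < 50 > 100". Pulse and temperature have fixed limits of the same kind.

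The section does not say that the counted value must be post-baseline or on treatment. It does not say how a subject already outside the limits at OLE baseline is handled, and it sets no size of change. Section 5.4 states that "The OLE baseline is used for all safety analyses", but nothing in 5.4.5 brings that baseline into the count.

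**The concern.** Long-term safety and tolerability is the primary objective of the extension (Section 3.1.1), and vital signs are among the primary endpoints (Section 5.1.1). A reader will take a count of notable values as a statement about what happened on drug. As written, it also counts subjects who entered outside the limits and stayed there.

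Section 5.4 says the safety analysis follows the Core Study. The Core Study was double-blind with a placebo group, so background out-of-range values could be compared between arms. In the extension every subject receives elenbecestat 50 mg (Section 3.2), and the columns show only earlier treatment. OLE baseline is the one reference left, and this count does not use it.

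For weight there is a second problem. Fixed limits as far apart as 45 and 100 kg say little about loss in an individual, so the number of subjects with a large loss does not appear in any vital-signs display that the SAP describes.

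**Working it through.** The plan states no figure on this point, so there is none to reproduce. The inputs are the Table 1 limits in Section 5.4.5. The baseline and follow-up values below are illustrative assumptions, because the SAP gives no distribution of weight or blood pressure.

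**1. Weight loss needed to reach the low limit.** For baseline weight B, the largest loss that stays unflagged is (B − 45)/B.

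| Baseline (kg) | Calculation | Largest unflagged loss | Weight after a 15% loss (kg) | Flag after a 15% loss |
|---|---|---|---|---|
| 50 | 5/50 | 10.0% | 42.5 | low |
| 60 | 15/60 | 25.0% | 51.0 | none |
| 70 | 25/70 | 35.7% | 59.5 | none |
| 80 | 35/80 | 43.8% | 68.0 | none |
| 90 | 45/90 | 50.0% | 76.5 | none |
| 100 | 55/100 | 55.0% | 85.0 | none |

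A 15% loss is flagged as low only if 0.85 × B < 45, that is, for B below 45/0.85 = 52.9 kg. A fall from 80 to 65 kg, 15/80 = 18.8%, is not flagged.

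**2. What the limits do to baseline and follow-up pairs.**

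| Measure | Baseline | Follow-up | Change | Flag at follow-up |
|---|---|---|---|---|
| Weight (kg) | 105 | 105 | 0% | high |
| Weight (kg) | 110 | 102.3 | −7.0% | high |
| Weight (kg) | 115 | 98 | −14.8% | none (high at baseline) |
| Weight (kg) | 48 | 44.6 | −7.1% | low |
| Systolic BP | 162 | 162 | 0 | high |
| Systolic BP | 165 | 161 | −4 | high |
| Systolic BP | 158 | 161 | +3 | high |
| Systolic BP | 110 | 159 | +49 | none |

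Stable and improving subjects are flagged, and some large changes are not. New crossings of a limit are flagged too (48 to 44.6 kg, 158 to 161), so the count is a mixture.

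**3. Size of the background.** The reported share equals the share with a new exceedance plus the share already outside at baseline who remain outside. The second term is added one for one. It is 0 if nobody starts outside, and 10 percentage points if 10% start above 100 kg and stay there (an assumption). The SAP gives no figure to narrow this range.

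**4. Comparison with the other subject-level safety summaries in the SAP.**
- Adverse events (5.4.2) must emerge, re-emerge or worsen relative to the OLE pretreatment state.
- The C-SSRS summary (5.4.3) is limited to ideation or behavior that is new or has worsened.
- Markedly abnormal laboratory values (5.4.4) require "a post-baseline value with an increase from baseline to a grade of 2 or higher", or to grade 3 for phosphate, and shift tables are added.
- ECG (5.4.6): interpretation has shift tables. The QTcF count is restricted to post-baseline results in the treatment period, and its absolute limits are accompanied by increases above 30 and 60 msec.
- Microhemorrhages (5.4.7) have a shift table.
- Vital signs (5.4.5) have none of these features.

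**The case against.** Much of the opposing case stands and sets the limits of the point.

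- **Change is reported elsewhere.** Section 5 requires minimum and maximum for all continuous variables, and 5.4.5 applies descriptive statistics to change by visit. A fall from 80 to 65 kg would make the minimum change at that visit −15 kg or lower. A reader might infer that large weight loss would go unseen; the documents do not support that. What is missing is the number of subjects beyond a given change.
- **New exceedances are counted.** A reader might infer that the table shows only who was out of range at entry. It does not: a subject moving from 130 to 165 mmHg systolic is counted. For pulse and temperature, which fluctuate, a stable background is a weak argument.
- **Absolute limits are not wrong in themselves.** The QTcF categories above 450, 480 and 500 msec in 5.4.6 are also absolute and carry no baseline condition. The difference is that change categories stand beside them.
- **No conclusion is said to rest on this count.** It supplements the change summaries, the phase is descriptive, and treatment-emergent adverse events would capture a weight or blood pressure change that an investigator reported. To say that the vital-sign data cannot support a safety conclusion would go too far.
- **Shells and programming specifications are separate documents** (Sections 9 and 11) and may add a condition. That limits certainty. But the SAP itself states the laboratory and QTcF rules, so the vital-sign rule belongs there too.

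**Conclusion.** The point holds for the subject-level count in 5.4.5 and no further. As written, the count cannot separate pre-existing from new out-of-range values, and no control arm offsets the background. For weight, the loss needed to trigger the low flag runs from just over 10% at 50 kg to just over 55% at 100 kg, so detection depends on starting weight rather than on change. The statement that large losses are missed in most subjects assumes that most weigh well above the 45 kg limit; for a 15% loss, that means at least 52.9 kg. Light subjects can still be flagged.

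The example weights and pressures are assumptions, and the size of the background cannot be estimated from the SAP. This is a cheap improvement to a display for a primary endpoint. It does not invalidate the vital-sign analysis.

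**What to change.** In Section 5.4.5:

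1. Keep Table 1, but define the count as subjects with at least one post-baseline on-treatment value outside the limits. State whether unscheduled visits count and which cut-off after the last dose applies.
2. Show that count against OLE baseline status in a low/normal/high shift table. Do not restrict it to subjects in range at baseline: that would drop someone who starts at 162 mmHg systolic and rises to 200, whereas the laboratory rule keeps subjects who worsen from an abnormal grade.
3. Add a pre-specified change-from-baseline category, at least for percent weight change, as 5.4.6 already does for QTcF. The sponsor should choose and justify the cut-off; the SAP offers none for vital signs. The shift table keeps subjects who start high in view but leaves them in the same cell when they rise further, so a change category for blood pressure is worth considering as well.

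The cost is a few sentences in the SAP, one or two more tables and minor programming. No new data are needed, and the limits shared with the Core Study are retained.

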#### 5.4.6 Electrocardiograms

Descriptive statistics for ECG parameters and changes from baseline will be presented by visit for treatment group by core study treatment (placebo and elenbecestat total) and combined total. Shift tables will present changes from baseline in ECG interpretation (categorized as normal; abnormal, not clinically significant; abnormal, clinically significant) to each post-baseline visit and to the end of treatment visit and the 12 week Follow-up visit.

In addition, the number (percentage) of subjects with at least 1 post-baseline abnormal ECG result in QTcF during the treatment period will be summarized. Clinically abnormal ECG results in QTcF will be categorized as follows:

Absolute QTcF interval prolongation:

- QTcF interval >450 msec

- QTcF interval >480 msec
- QTcF interval >500 msec

Change from baseline in QTcF interval:

- QTcF interval increases from baseline >30 msec
- QTcF interval increases from baseline >60 msec

#### 5.4.7 Safety MRI

Vasogenic Edema and white matter disease will be summarized by visit for treatment group by core study treatment (placebo and elenbecestat total) and combined total. Shift table for the total number of microhemorrhages will be presented by visit for treatment group by core study treatment (placebo and elenbecestat total) and combined total. Other abnormalities will be presented in subject data listing.

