### 5.1 Study Endpoints

#### 5.1.1 Primary Endpoints

- Safety endpoints: adverse event (AE), vital sign, electrocardiogram (ECG), physical examination, clinical laboratory test, any relevant test of cognitive function to evaluate decline, and magnetic resonance imaging (MRI) parameter (microhemorrhage, vasogenic edema, and other clinically significant abnormalities).

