### 8.3 Definition of visit windows

The protocol specified visits/weeks and corresponding time windows used for visit-wise analyses are presented in terms of days relative to the first dose in the OLE.

Different assessments may have different visit schedules. A general rule for determining a time window for each scheduled visit is to split the two consecutive scheduled visits in the middle point of the two consecutive visits. For example, the time window for visit X is from the middle point between visit (X-1) and X (exclusive) to the middle point between visit X and (X+1) (inclusive). The time window for the first post-baseline visit is from the next day of the first dose. . The details will be specified in the programming specification.

In addition, the following visits will be assigned separately (for MMSE, FAQ, and safety endpoint) if last dose date is not missing.

- Last on treatment: the last post-baseline assessment on or before last dose date.
- End of treatment: the earliest assessment on or after last dose date and before last dose date + 56 days (inclusive)
- 12 week Follow-up: the closest assessment to last dose date + 84 days after last dose date + 57 days (inclusive)

The assessments after last dose date + 8 days (inclusive) will not be included in the visit-wise analyses except end of treatment visit and 12 week Follow-up visit (the analysis flag should not be “Y”). If last dose date is missing, the assessment at early discontinuation from study drug, follow-up visits and unscheduled visits on or after early discontinuation from study drug or follow-up visits will not be included in the visit-wise analyses.

For biomarker endpoints, the following allowance after last dose date will be used. The assessments out of each allowance will not be included in the visit-wise analyses.

- Plasma Ab(1-x): last dose days + 5 days (inclusive)
- vMRI: no limitation (all assessments will be included)

If last dose date is missing, the assessment at early discontinuation from study drug, follow-up visits and unscheduled visits on or after early discontinuation from study drug or follow-up visits will not be included in the visit-wise analyses for Plasma Ab(1-x).

If there are multiple assessments for one analysis visit, the following rules will be applied in order to select one assessment.

1. Pick the closest assessment to the target day
2. Pick the assessment at scheduled visit than unscheduled visit

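### Safety MRI has no any-time count of subjects with new vasogenic edema or more microhemorrhages, and by-visit selection can leave a transient positive scan out of the MRI tables

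*SAP*

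**What the plan says.** SAP section 5.1.1 includes in the primary safety endpoints the "magnetic resonance imaging (MRI) parameter (microhemorrhage, vasogenic edema, and other clinically significant abnormalities". Section 5.4 places the imaging among "changes from baseline in laboratory safety test variables, ECGs, safety MRI, vital sign measurements", whereas its incidence items are adverse events, laboratory, ECG, vital signs and suicidality.

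Section 5.4.7 then fixes the output:

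- For edema: "Vasogenic Edema and white matter disease will be summarized by visit for treatment group by core study treatment".
- For microhemorrhages: "Shift table for the total number of microhemorrhages will be presented by visit for treatment group by core study treatment".
- For the rest: "Other abnormalities will be presented in subject data listing".

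Section 8.3 decides which scan fills a by-visit cell. Windows run from midpoint to midpoint between scheduled visits. "If there are multiple assessments for one analysis visit, the following rules will be applied in order to select one assessment": first, "Pick the closest assessment to the target day"; next, "Pick the assessment at scheduled visit than unscheduled visit"; last, the earliest on the day. For safety endpoints it also defines Last on treatment, End of treatment and 12 week Follow-up slots when the last dose date is known. Other assessments from 8 days after the last dose are left out of the visit-wise analyses. The exemption from any such limit is given to volumetric MRI, under the biomarker endpoints, and not to safety MRI.

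**The concern.** There are two separate gaps.

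The first is that no per-subject count exists. The basic safety question for an imaging finding is how many subjects developed it on treatment, and by-visit cells do not answer that. For edema, 5.4.7 does not specify a shift from baseline either, so edema already present and new edema are not separated there. This gap remains even if no unscheduled MRI was ever done.

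The second is that a positive scan may not reach the tables. The selection rule takes no account of the result. An unscheduled scan that shows edema can give way to a negative scheduled scan nearer the target day once the edema has resolved. Section 5.4.7 promises a listing only for other abnormalities, so it does not assure that the displaced scan is shown anywhere in the MRI output.

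At stake is an understated frequency for findings that the plan itself names as primary safety endpoints.

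**Working it through.** The SAP states no MRI rate, sample size or schedule on this point, so there is no figure to reproduce. The check sets the sections side by side and then applies the 8.3 rules to assumed scan dates.

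**1. Comparison with other safety domains**

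| Domain | Any-time or incidence count of subjects? |
|---|---|
| QTcF (5.4.6) | Yes: at least one abnormal post-baseline result in the treatment period |
| Laboratory TEMAVs (5.4.4) | Yes: increase in grade from baseline, each subject once per parameter and direction |
| C-SSRS (5.4.3) | Yes: incidence of new or worsening ideation or behavior |
| Vasogenic edema (5.4.7) | No: by visit only |
| Microhemorrhage (5.4.7) | No: by-visit shift only |

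**2. By-visit cells do not give the number of subjects.** Suppose one subject is positive at month 12 and one at month 24. If this is the same person, 1 subject is affected; if not, 2 are. The cells read 1 and 1 in both cases. In general the number of subjects shown positive lies anywhere between the largest cell and the sum of the cells.

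**3. Worked selection (assumed 12-monthly MRI, targets day 365 and day 730).** The scans are day 370 scheduled negative, day 450 unscheduled positive and day 735 scheduled negative, all on treatment.

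- The midpoint is (365 + 730)/2 = 547.5, so the first window is day 2 to 547.
- Distances to target in that window are |370 − 365| = 5 and |450 − 365| = 85. Day 370 is selected.
- In the next window, day 735 is the only scan and is selected.
- Last on treatment is day 735 or a later scan, so that slot does not recover day 450.

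The subject is counted 0 times by visit and 1 time under an any-time count. If dosing had ended between day 450 and the next scan, day 450 would have been the Last on treatment assessment.

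**4. How the loss depends on schedule and duration.** Let I be the interval between scheduled scans and d the duration of the finding, both assumed. If the unscheduled scan loses the selection, the finding appears only when a scheduled scan falls while it is present. The missed share is then about 1 − d/I for d < I. For I = 365 and d = 90 this is 1 − 90/365 = 75%; for I = 730 and d = 30 it is 1 − 30/730 = 96%.

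A simulation of the full selection order, with 8,000 subjects per cell, agrees closely. Its assumptions are one transient finding per subject with onset uniform over 48 months, one positive unscheduled scan within 14 days of onset, and scheduled scans within 10 days of target.

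| Scheduled MRI | 30-day finding | 90-day finding | 180-day finding |
|---|---|---|---|
| 3-monthly | 65% | 2.5% | 0% |
| 6-monthly | 83% | 49% | 2% |
| 12-monthly | 92% | 75% | 50% |
| 24-monthly | 96% | 87% | 75% |

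These are shares of subjects who already have such a finding and such a scan. They are not estimates of how often that happens in this trial. The simulation does not model the three extra slots and assumes attendance at every scheduled scan. Displaying those slots could only lower the shares. An any-time count that uses all scans misses 0% by construction.

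**The case against.** The strongest case on the other side has four parts.

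**Selection applies only when a window holds several scans.** A reader might infer that every finding seen on an off-target unscheduled scan is lost, or that the rule removes the scans most likely to be positive. The text does not support either. A scan alone in its window is kept however far it lies from the target. Closeness to target ignores both result and scan type, and preference for the scheduled scan is only a tie-break. A positive unscheduled scan nearer the target displaces a negative scheduled one. This stands. It is true only that the number of subjects ever shown positive cannot exceed the number who had a positive scan; prevalence at a given visit can move either way.

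**The extra slots may retain some scans.** The SAP says that the study was terminated, so the last scan on treatment may often be off schedule, and Last on treatment would take it. This stands in part: 5.4.7 does not say that it displays these slots, whereas 5.4.4 and 5.4.6 name end of treatment and 12-week follow-up. Within End of treatment the earliest assessment is used, so a later positive scan in that window is passed over.

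**Findings may reach the adverse event tables.** Section 5.4.2 counts each subject once per term, free of visit windows, and lists all adverse events. This also stands, so the loss concerns the MRI tables and not necessarily the whole report. However, the SAP neither requires MRI findings to be recorded as adverse events nor defines which events are of specific interest.

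**Details may sit elsewhere.** Table shells, programming specifications and the protocol are separate, and listing other abnormalities does not exclude a listing of edema. That is fair, but 5.4.7 is where the analysis of these endpoints is fixed, and it fixes by-visit output.

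Microhemorrhages that persist would usually show at the next scheduled scan. For them the missing per-subject count is the main issue.

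**Conclusion.** The point holds in a bounded form. It is certain from the text that 5.4.7 gives no number of subjects with new or worsened vasogenic edema, or with an increased microhemorrhage count, at any time after OLE baseline. It is also certain that a positive scan can be absent from the MRI tables under 8.3, mainly for edema that resolves between scheduled scans.

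How often that happens cannot be determined from the SAP. The 0% to 96% range depends on the assumed schedule and duration and on the assumption that an unscheduled positive scan exists. It shows that the loss can range from nothing to nearly all such cases, and no more. The plan should be amended, because following it as written can understate a primary safety endpoint and the remedy is cheap. In a descriptive, terminated, open-label extension this is an improvement to the reporting and does not invalidate the safety analysis.

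**What to change.** Add to section 5.4.7:

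- The number (%) of subjects with any new or worsened vasogenic edema relative to OLE baseline, and the number (%) with any increase in total microhemorrhage count from OLE baseline.
- The source: all post-baseline safety MRIs, including unscheduled and early-discontinuation scans, without the one-scan-per-visit selection.
- The denominator: subjects with a baseline and at least one post-baseline safety MRI, in the existing groups (core placebo, core elenbecestat total, combined total).
- A listing of all scans positive for these two findings, with study day.

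Keep the by-visit summary and shift table as supportive. White matter disease is not named in the primary endpoint and can stay by visit. The cost is one extra table and one listing from data already collected.
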